PRIMARY ENDPOINT	The primary outcome will be fluvastatin AUC0-12h and AUC0- $\infty$ (AUC = area under the plasma concentration versus time curve).
SECONDARY ENDPOINTS	Secondary outcomes will include fluvastatin maximum plasma concentration (Cmax) and time to Cmax (Tmax) .
SAFETY EVALUATIONS	Safety evaluation will be determined by the incidence of adverse events. Subjects will be monitored on an ongoing basis while involved with the study by study personnel. Subjects will be screened with a medical history and physical examination by the study physician and have screening hematology, chemistries, liver, renal and coagulation laboratories. Subjects must have normal function of all major organs. At study completion, subjects will have repeat physical examination and repeat hematology, chemistries, liver, renal and coagulation laboratories for safety monitoring.
PLANNED INTERIM ANALYSES	Serious adverse events will be monitored by the committee on an ongoing basis throughout the study.
STATISTICS Primary Analysis Plan	AUC0- $\infty$ will be calculated using the trapezoidal rule from time 0 to Clast + Clast/ke. Parameters such as maximum plasma concentration (Cmax) and time to Cmax (Tmax) will be determined from the observed data. The terminal elimination rate constant (ke) will be obtained using linear regression of log transformed concentrations over the terminal log-linear decline phase. Oral clearance (CL/F) will be calculated using Dose/AUC0- $\infty$ . Other estimated pharmacokinetic parameters will be calculated using non-compartmental methods with

	WinNonlin Professional software (Pharsight, Inc., Mountain View, CA). Log-transformed pharmacokinetic parameters will be compared across treatments with analysis of variance for repeated measures. Differences will be regarded as statistically significant if $p < 0.05$ . Data will be presented as mean values with standard deviations. Each subject will serve as his/her own control. Differences in pharmacokinetic parameters between treatments will be calculated using student's paired t-test. Statistical calculations will be done using STATA 10.0 (StataCorporation, College Station, TX).

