### 1.2 Overview of Clinical Studies

Contrary to our expectations, one clinical study has demonstrated that co-administration of single-dose rifampin with 2 mg of fluvastatin results in significant increase in exposure of the cholesterol-lowering agent. However this study was conducted with one tenth to one

fortieth of the common dose of fluvastatin, and we believe that the effect of rifampin on fluvastatin exposure in this study to be due to the low concentration of fluvastatin.

Clinical studies have demonstrated that co-administration of single-dose rifampin with the BDDCS Class II drug atorvastatin results in marked increases in concentrations of the cholesterol-lowering agent. Similar studies with the BDDCS class III drug rosuvastatin and class II drug glyburide showed similar transporter effects which increased plasma concentrations of the two drugs when co-administered with a single dose of rifampin. These studies have demonstrated the significant effects of hepatic uptake transporters on the pharmacokinetics of BDDCS class II and III drugs. It is expected that these transporter effects will not be significant for BDDCS class I drugs like fluvastatin.

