## 3 STUDY OBJECTIVES

### 3.1 Primary Objective

The primary objective is to determine whether or not inhibition of OATP1B1-mediated drug transport of fluvastatin will be clinically significant. The study will assess if a IV dose of rifampin (to inhibit hepatic uptake transporters) immediately prior to oral fluvastatin dosing will have any effect on fluvastatin total drug exposure.

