### **15.3 Analysis of Primary Endpoint**

AUC0-∞ will be calculated using the trapezoidal rule from time 0 to Clast + Clast/ke. Parameters such as maximum plasma concentration (Cmax) and time to Cmax (Tmax) will be determined from the observed data. The terminal elimination rate constant (ke) will be obtained using linear regression of log transformed concentrations over the terminal log-linear decline phase. Oral clearance (CL/F) will be calculated using Dose/AUC0-∞. Other estimated pharmacokinetic parameters will be calculated using non-

compartmental methods with WinNonlin Professional software (Pharsight, Inc., Mountain View, CA). Log-transformed pharmacokinetic parameters will be compared across treatments with analysis of variance for repeated measures. Differences will be regarded as statistically significant if  $p < 0.05$ . Data will be presented as mean values with standard deviations. Each subject will serve as his/her own control. Differences in pharmacokinetic parameters between treatments will be calculated using student's paired t-test. Statistical calculations will be done using STATA 10.0 (StataCorporation, College Station, TX).

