	
be calculated using Dose/AUC0-∞. Other estimated pharmacokinetic parameters will be calculated using non-compartmental methods with WinNonlin Professional software (Pharsight, Inc., Mountain View, CA). Log-transformed pharmacokinetic parameters will be compared across treatments with analysis of variance for repeated measures. Differences will be regarded as statistically significant if <math>p < 0.05</math>. Data will be presented as mean values with standard deviations. Each subject will serve as his/her own control. Differences in pharmacokinetic parameters between treatments will be calculated using student's paired t-test. Statistical calculations will be done using STATA 10.0 (StataCorporation, College Station, TX).

Rationale for Number of Subjects	
Using a paired t-test and prior data, a sample size of <math>n=10</math> in each group is needed to detect a 50% difference in AUC(0-12) between the two study regimens with a statistical power of 80% (two sided alpha = 0.05) and standard deviation of 50%. Due to the lesser effects of rifampin on fluvastatin AUC, the within subject variability can affect the sample size. We plan to enroll sample size of 12 subjects to maintain an adequate sample size in case of potential attrition.

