## 3. STUDY OBJECTIVES

### 3.1 Primary Objective

The primary objective is to determine whether or not inhibition of OATP1B1-mediated drug transport of fluvastatin will be clinically significant when hepatic enzymes are induced.

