## 15.3 Analysis of Primary Endpoint

AUC0-∞ will be calculated using the trapezoidal rule from time 0 to Clast + Clast/ke. Log-transformed pharmacokinetic parameters will be compared across treatments with analysis of variance for repeated measures. Differences will be regarded as statistically significant if p< 0.05. Data will be presented as mean values with standard deviations. Each subject will serve as his/her own control. Differences in pharmacokinetic parameters between treatments will be calculated using student's paired t-test. Statistical calculations will be done using STATA 10.0 (StataCorporation, College Station, TX).

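### Both protocols ask whether the effect is clinically significant and expect that it is not, but the only decision rule is a p<0.05 difference test, which cannot support that conclusion

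*Combined protocol and SAP*

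**What the plan says.** The combined document holds two protocols, one giving single-dose rifampin and one in subjects pre-induced with oral rifampin. Section 3.1 of the single-dose protocol states: "The primary objective is to determine whether or not inhibition of OATP1B1-mediated drug transport of fluvastatin will be clinically significant". It then asks whether IV rifampin "will have any effect on fluvastatin total drug exposure". Section 3.1 of the induced-state protocol asks only whether the inhibition "will be clinically significant when hepatic enzymes are induced".

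Section 1.2 of both protocols states the expected answer: "It is expected that these transporter effects will not be significant for BDDCS class I drugs like fluvastatin". The induced-state protocol adds that the AUC ratio with and without IV rifampin should be nearer 1 than the ratio of about 2 reported for glyburide.

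The analysis is the same in both: "Log-transformed pharmacokinetic parameters will be compared across treatments with analysis of variance for repeated measures", with a paired t-test also named. The criterion in section 15.3 of the single-dose protocol is "Differences will be regarded as statistically significant if" p<0.05, and section 15.3 of the induced-state protocol has the same rule: "Differences will be regarded as statistically significant if p< 0.05". On reporting, the plan says "Data will be presented as mean values with standard deviations".

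Section 15.6 sizes each study to detect a 50% difference in AUC0-12 with SD 50%, 80% power and two-sided alpha 0.05. This gives 10 subjects, with 12 to be enrolled. Section 15 of each protocol defers detail to a later SAP.

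**The concern.** The rule and the objective do not match, in either direction. A p-value above 0.05 says only that zero difference was not rejected, which in a small study is compatible with effects that might matter. A p-value below 0.05 says the effect is probably not zero, not that it is large enough to matter. Neither protocol states how large a change in AUC would be clinically significant, so neither outcome answers the main question.

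The expected result is exactly the one the analysis cannot establish. Section 15.6 itself refers to rifampin having a smaller effect on fluvastatin AUC, without giving a figure, yet plans for 50%. If non-significance were read as confirmation, limited power would favour the investigators' hypothesis. The single-dose protocol also means to use its result as a test of the BDDCS (section 2), so a wrong reading would carry beyond this drug pair.

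**Working it through.** **Inputs.** From section 15.6 of both protocols: difference 50%, SD 50%, two-sided alpha 0.05, n = 10 needed, 12 enrolled. From section 15.3: analysis on the log scale. Assumed, because the documents give no value: the SD of within-subject log differences, and every candidate no-effect range.

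**Step 1: reproduce the plan's sample size.** Paired t-test, df = n − 1, non-centrality = √n × difference/SD. With 0.50/0.50 = 1, this is √10 = 3.16 and the power is 80.3%. With n = 9 it is 74.8%, so 10 is the smallest n reaching 80%. With 12 the power is 88.3%. The arithmetic is sound and reads the 50% as the SD of the within-subject difference.

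**Step 2: chance of p>0.05 when there is a real effect, on the plan's scale.** For a 25% difference, the ratio to the SD is 0.25/0.50 = 0.5 and the non-centrality is 0.5 × √10 = 1.58 or 0.5 × √12 = 1.73.

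| True difference | n = 10 | n = 12 |
|---|---|---|
| 25% (illustrative) | 71% | 65% |
| 50% (planning value) | 20% | 12% |

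**Step 3: the same on the planned log scale.** Converting a 50% CV gives SD = √ln(1 + 0.5²) = √ln 1.25 = 0.472. The effects are ln 1.25 = 0.223 and ln 1.5 = 0.405.

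| True AUC ratio | Log SD | n = 10 | n = 12 |
|---|---|---|---|
| 1.25 | 0.472 | 73% | 68% |
| 1.25 | 0.35 to 0.50 | 56 to 76% | 48 to 71% |
| 1.5 | 0.472 | 32% | 23% |
| 1.5 | 0.35 to 0.50 | 10 to 37% | 5 to 27% |

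**Step 4: the largest observed ratio that is still non-significant.** This is exp(t × SD/√n), with t the 97.5% point on n − 1 df and SD 0.472.
- n = 10: exp(2.262 × 0.472/√10) = exp(0.338) = 1.40.
- n = 12: exp(2.201 × 0.472/√12) = exp(0.300) = 1.35.

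An observed increase of 35 to 40% could therefore end as p>0.05.

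**Step 5: what an interval rule would do.** The rule is that the whole 90% CI of the ratio must lie inside the no-effect range, with SD 0.472 and true ratio 1.

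| Illustrative range | n = 10 | n = 12 | Completers for 80% |
|---|---|---|---|
| 0.67 to 1.50 | 61% | 74% | 14 |
| 0.80 to 1.25 | 5% | 8% | 40 |

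With SD 0.50 the completers needed become 15 and 45; with SD 0.3 they become 7 and 17. With 0.67 to 1.50 and a true ratio of 1.5, the rule would wrongly declare no relevant effect in 5% of trials. That figure follows from the design of the rule, because 1.5 is its limit; it bounds the error that the p<0.05 rule leaves open.

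**The case against.** No sentence says that p>0.05 will be read as absence of a clinically significant effect; section 15.3 says only when a difference counts as statistically significant. The single-dose protocol does ask about any effect, and there the test fits: a clear p<0.05 could contradict the BDDCS prediction, a live possibility since section 1.2 cites an increase in exposure at 2 mg fluvastatin. Sections 2 and 4.1 of the induced-state protocol also speak of evaluating effects. A SAP is promised, the log-scale model would yield a ratio and interval directly, and these are small mechanistic studies. The 25% effect and the log SDs are not the plan's, and at the 50% it does name, the miss rate on its own scale is only 20% or 12%.

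Much of this is fair, and it limits the point. The test should stay for the any-effect question. The magnitudes depend on assumptions, and at log SD 0.35 with 12 subjects a ratio of 1.25 is missed slightly less than half the time (48%). But the stated primary objective in both protocols is clinical significance, and no written rule answers it. Sections 2 and 4.1 of the induced-state protocol are not its objective. Neither protocol commits the SAP to a threshold or an interval, and a range chosen after results are seen would carry little weight. The 50% in section 15.6 is a detectable difference and is never called the clinical threshold.

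**Conclusion.** The concern holds and should be fixed before any concentration results are seen. Following the plan exactly leaves the expected conclusion unsupported in both protocols. In the induced-state protocol the rule does not answer the stated objective at all; in the single-dose protocol it answers only the secondary sentence about any effect.

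That conclusion is logical and does not depend on a particular effect size. The risk of a non-significant result despite a 25% effect is about two in three or more on the plan's own SD, and 48 to 76% over log SDs of 0.35 to 0.50. These figures use a one-sample t-test on within-subject differences with n − 1 df and no period term. The sample-size calculation itself is not in dispute.

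**What to change.** In section 15.3 and the synopsis of both protocols, and in the promised SAP:

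1. Make the primary result the fluvastatin AUC geometric mean ratio (with versus without IV rifampin) with its 90% CI, from the log-scale model already planned.
2. Have the sponsor pre-specify and justify a no-effect range. The 50% used for sample size is not by itself a justification.
3. Conclude no clinically significant effect only if the whole 90% CI lies inside that range, for both AUC measures if both stay primary.
4. Keep the p<0.05 test (95% CI excluding 1) for the any-effect question, reported with the ratio and interval, and do not call an effect clinically significant on the p-value alone.
5. Otherwise report the result as inconclusive, with its interval.
6. State that p>0.05 alone will not be read as absence of effect.

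The direct cost is wording, with no new data or samples. The real cost is that the trial may be inconclusive: with a narrow range such as 0.80 to 1.25, 10 to 12 subjects would rarely suffice unless within-subject variability is well below the planning value. The sponsor should see the figures in step 5 when choosing the range, and check the sample size against it. The comparison of ratios between induced and uninduced states, which the induced-state protocol wants, has no planned analysis and is not covered by this change.

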## 4 STUDY DESIGN

### 4.1 Study Overview

The effect of rifampin on the pharmacokinetics of fluvastatin will be studied in healthy volunteers in a two-period, randomized, unblinded, crossover clinical trial. On period 1 of the study, subjects will be randomized to one of two treatment groups:

- (i) one oral dose of fluvastatin (Lescol®) 20mg capsule
- (ii) one oral dose of fluvastatin (Lescol®) 20mg capsule immediately following a 30-min intravenous infusion of rifampin 600mg in 10ml Normal Saline.

The two study periods will preferentially be on a Tuesday and Thursday, separated by one day of washout. Subjects will be instructed to fast overnight the day before study periods 1 and 2, and for 3h post-dosing. In both treatments, venous blood samples (~8ml each) will be drawn at 0, 0.33, 0.67, 1, 1.5, 2, 2.5, 3, 4, 6, 9, 12h after fluvastatin dosing. Period 2 will begin after at least a 1-day washout when subjects will receive the second treatment, followed by blood draws at the same time points as after fluvastatin dosing alone.

	Period 1	Period 2
Group 1	A	B
Group 2	B	A

A= fluvastatin; B =rifampin +fluvastatin

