## **8 STUDY TREATMENTS**

### **8.1 Method of Assigning Subjects to Treatment Groups.**

Once included in the study, patients will be randomized using computer-generated random numbers, corresponding to each treatment. This will be performed by someone other than the investigator and will ensure equal number of patients in each treatment sequence.

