### **12.3 Replacement of Subjects**

Subjects who withdraw from the study treatment will be replaced.

Subjects who withdraw from the study will be replaced.

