### **15.1 Data Sets Analyzed**

All eligible patients who are randomized into the study will be included in the data analysis.

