## 4. STUDY DESIGN

### 4.1 Study Overview

The effect of rifampin on the pharmacokinetics of fluvastatin under a hepatic enzyme induced state will be studied in healthy volunteers in a two-period, randomized, unblinded, crossover clinical trial. For the first 5 days of the trial, the patients will be pretreated with 600mg oral rifampin (two 300mg rifadin capsule) once daily to induce hepatic enzymes (and transporters). For study period 1, subjects will be randomized to one of two treatment groups:

- (i) one oral dose of fluvastatin (Lescol®) 20mg capsule
- (ii) one oral dose of fluvastatin (Lescol®) 20mg capsule immediately following a 30-min intravenous infusion of rifampin 600mg in 10ml Normal Saline

The two study periods will ideally be on a Tuesday and Thursday, separated by one day of fluvastatin washout. The oral food intake will be standardized and subjects will be instructed to fast overnight the day before study period 1 and period 2, and for 3h post-dosing. In both treatments, venous blood samples (8ml each) will be drawn at 0, 0.33, 0.67, 1, 1.5, 2, 2.5, 3, 4, 6, 9, 12h after fluvastatin dosing. During the 1 day of fluvastatin washout, patients will continue pretreatment with one 600mg dose of oral rifampin. Period 2 will begin after 1 day of fluvastatin wash out, when subjects will receive the second treatment, followed by blood draws at the same time points after fluvastatin dosing. If study period two does not follow one day after study period one, it will most likely be conducted on Tuesday or

Thursday of the following week. In this case, the subjects would be maintained in a state of induction of hepatic enzymes by the same preinduction regimen with 600 mg of oral rifampin for 5 days before study period 2.

	Period 1	Period 2
Group 1	A	B
Group 2	B	A

A= fluvastatin; B =rifampin +fluvastatin

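### Both AB/BA crossover protocols name two unranked tests, one of unstated scale and neither with a period term; a single period-adjusted log-scale model should be primary

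*Combined protocol and SAP*

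**What the plan says.** Both protocols use the same AB/BA layout. Section 4.1 of each says that the effect of rifampin "will be studied in healthy volunteers in a two-period, randomized, unblinded, crossover clinical trial", and section 8.1 of each says that the randomisation "will ensure equal number of patients in each treatment sequence".

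For the analysis, section 15.3 and the synopsis of each protocol contain two sentences:

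- "Log-transformed pharmacokinetic parameters will be compared across treatments with analysis of variance for repeated measures"
- "Differences in pharmacokinetic parameters between treatments will be calculated using student's paired t-test"

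The first gives a scale (log) but no model factors. The second gives neither. Nothing says which is primary. Section 15.4 names no between-treatment test, so these two sentences are also the only planned comparison for Cmax, Tmax and CL/F. Results are to be presented as means with standard deviations and judged at p < 0.05; no ratio or confidence interval is specified.

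Three other passages bear on the point. Section 15.1: "All eligible patients who are randomized into the study will be included in the data analysis". Section 12.3: "Subjects who withdraw from the study will be replaced". Section 15 promises a SAP that may modify the analysis, but no text in the documents settles the model. Section 15.6 bases the sample size on a paired t-test: n = 10 for a 50% difference in AUC0-12 with an SD of 50%, and 12 to be enrolled.

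**The concern.** In an AB/BA design with both sequences filled, a period difference can be separated from the treatment effect. Leaving it out moves any period difference into the error term. Power then falls and the test becomes conservative. That direction matters because both protocols expect rifampin to have little effect on fluvastatin (section 1.2), and a less sensitive test favours that expected result.

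The unstated scale leaves a choice that could be made after the data are seen: a t-test on raw AUC and an ANOVA on log AUC need not agree at the 5% level. A paired t-test also drops anyone with only one evaluable period, which does not fit section 15.1.

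The induced-state protocol shows one difference between periods. Before Period 1: "For the first 5 days of the trial, the patients will be pretreated with 600mg oral rifampin". Before an on-schedule Period 2: "During the 1 day of fluvastatin washout, patients will continue pretreatment with one 600mg dose of oral rifampin". That is 5 oral doses before Period 1 and 6 before Period 2. The protocol does not say whether induction is stable after 5 doses. It also wants AUC ratios compared between induced and uninduced states (section 1.2), and for that a ratio with a confidence interval is the natural output.

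**Working it through.** **1. The plan's own figure.** Inputs from section 15.6: difference 50%, SD 50%, two-sided alpha 0.05, power 80%. Paired t-test, df = n − 1, noncentrality = (0.50/0.50) × √n. Exact noncentral t gives 74.8% at n = 9 and 80.3% at n = 10. The stated 10 is reproduced if 50% is the SD of the paired difference and 10 is the total number of subjects.

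**2. Are the two named tests different?** With subject and treatment as the only factors, complete pairs and the same scale, F = t². A numerical check with 12 subjects gave p = 0.04886 from both. They can differ only through scale, an unstated factor or incomplete pairs.

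**3. Period-adjusted model.** The estimate is the mean of the two sequence means of the within-subject log differences. SE = SD × √[(1/n₁ + 1/n₂)/4], with df = n − 2. At 6:6 this is 0.50 × √(0.3333/4) = 0.144, the same as SD/√12, so the only cost at equal sequences is one degree of freedom. Power with no period effect, SD of log differences 0.50 (assumed):

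| Completers | Effect 0.50: paired / adjusted | Effect ln 1.5 = 0.405: paired / adjusted |
|---|---|---|
| 6:6 | 88.3% / 87.6% | 72.5% / 71.7% |
| 5:5 | 80.3% / 79.1% | 62.8% / 61.5% |
| 6:4 | 80.3% / 77.4% | 62.8% / 59.7% |

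An effect of 0.50 on the log scale is a ratio of 1.65. It is the reading that reproduces the plan's figure; ln 1.5 is a 50% increase.

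**4. Leaving period out.** Let g be the Period 2 minus Period 1 difference on the log scale. The B − A difference is centred at d + g in sequence AB and d − g in BA. At equal sequences the mean remains d, but the expected variance of the differences is 0.50² + g² × n/(n − 1). For n = 12 and g = 0.2 this is 0.25 + 0.04 × 12/11 = 0.294, an SD of 0.542; for g = 0.3 the SD is 0.590. The documents give no g, so a range is shown (simulated, 6:6):

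| g | Paired power, d = 0.50 | Paired power, d = ln 1.5 | Paired type I error |
|---|---|---|---|
| 0 | 88% | 73% | 5.0% |
| 0.1 | 87% | 71% | 4.6% |
| 0.2 | 84% | 67% | 3.6% |
| 0.3 | 79% | 59% | 2.4% |

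The adjusted model keeps 87.6%, 71.7% and 5% throughout. Around an observed ratio of 1, the average 95% CI is exp(±0.314) = 0.73 to 1.37 adjusted. Unadjusted, it is exp(±0.337) = 0.71 to 1.40 at g = 0.2 and exp(±0.367) = 0.69 to 1.44 at g = 0.3.

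**5. Bias.** The unadjusted mean is off by g × (n₁ − n₂)/n. This is zero at equal sequences. At 6:4 it is 0.2 × g, so 0.04 to 0.06 on the log scale (about 4% to 6%) for g = 0.2 to 0.3.

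**6. Degrees of freedom.** If one-period subjects are included through a mixed model, a normal reference gives type I error of 7.8–8.0% at 6:6 and 8.4–8.8% with 10 completers. Kenward-Roger, or t on completers minus 2, gives 4.9–5.2% (simulated with g = 0.2 and between-subject SD 0.3 to 0.7, assumed). Adding one Period-1-only subject per sequence to 5:5 completers cuts the SE by only 0.9–2.5%.

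**7. What a period term cannot absorb.** In the induced-state protocol, BA subjects also receive IV rifampin in Period 1. Before an on-schedule Period 2 they have had 5 + 1 + 1 = 7 rifampin doses, against 5 + 1 = 6 in AB. The oral count differs by period; the IV dose differs by sequence.

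**The case against.** The benefit depends on a period effect that nobody has documented. The single-dose protocol shows no design reason for one: single doses, two study days, the same fasting rules. Gains appear only at g = 0.2 to 0.3, which is a 22% to 35% shift in AUC between two days. At g = 0 the adjustment loses a little power. The planned analysis is unbiased at equal allocation, does not exceed its nominal error rate, and withdrawals are replaced. A SAP is still to come. All of this stands, and it limits the point to efficiency and specification.

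It also stands that how 50% is read matters more than the period term. Moving from 0.50 to ln 1.5 costs about 16 points at 6:6 (88.3% to 72.5%). If 50% is a within-subject CV, the SD of log differences is √(2 × ln 1.25) = 0.668, and 12 completers give 65.6% paired or 64.8% adjusted for d = 0.50, and 48.3% or 47.6% for ln 1.5.

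The objection does not remove the unstated scale, the missing ranking, or the absence of a ratio with a CI. Nor does section 12.3 say that a replacement takes the withdrawn subject's sequence, so equal completers are not assured.

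**Conclusion.** The point holds as a cheap improvement that should be made before data are analysed. The two protocols leave open the scale of the t-test, the terms of the ANOVA, and which result decides. One period-adjusted log-scale model settles all three. Its size is conditional: negligible for g of 0.1 or less, and for g of 0.2 to 0.3 about 3 to 9 power points at 6:6 for d = 0.50 (87.6% against 84% and 79%) and about 5 to 13 for ln 1.5 (71.7% against 67% and 59%). These figures assume an SD of log differences of 0.50.

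A reader might infer four stronger things that the documents do not support:

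- That the planned test is invalid or biased. With the planned equal sequences it is unbiased and, at worst, conservative; bias needs unequal completers as well as a period effect.
- That the two named tests will conflict. On complete log data without a period term they are the same test.
- That the extra oral dose before Period 2 demonstrates a period effect. It is a reason to allow for one; its size, and whether induction has levelled off, are not stated.
- That a period term deals with carryover. It does not: the Period 1 IV dose differs by sequence, and no carryover claim is made here.

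**What to change.** In section 15.3 and the synopsis of both protocols, or in the promised SAP, replace the two test sentences with:

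> Log-transformed AUC0-12h and AUC0-∞ (primary) and Cmax and CL/F are each compared by a linear model with subject, period and treatment (complete pairs; t reference with number of completers minus 2 df). The rifampin + fluvastatin to fluvastatin geometric mean ratio is reported with its 95% CI. Tmax is compared by a nonparametric test on period differences between sequences.

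The secondary parameters must be named here, because the sentences being replaced are their only planned comparison. Ordinary least squares is enough for complete pairs, with exact n − 2 df. If one-period subjects are to be included, in line with section 15.1, use a mixed model with Kenward-Roger df or the same t reference, not a normal reference.

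Align the sample-size text in section 15.6 and the synopsis of both protocols with the new model. With an SD of the paired difference of 50%, it has 79.1% power at n = 10, just under the stated 80%, and 87.6% at the planned 12. The smallest n reaching 80% is 11, or 12 with equal sequences, so enrolment need not change.

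The cost is one degree of freedom. If there is no period effect, that is 0.6 to 0.9 power points at 6:6, 1.3 at 5:5 and about 3 at 6:4. Study conduct is unaffected.
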